The objective of Project 500 is to carefully analyze a complete set of multiple clinical and environmental questionnaires and selected infant biological samples pertinent to early clinical outcomes (up to age 1 year). The **primary clinical outcomes are recurrent episodes of wheezing and development of atopy by age 1 year**. Atopy is defined by skin allergen responses. Secondary outcomes include atopic dermatitis or eczema, and reported food allergy. We propose detailed exploration of patterns of clinical illnesses and will correlate these with analysis of multiple biomarkers to determine their predictive power.

There is good evidence from longitudinal epidemiological studies and from clinical trials that allergy is both a common precursor to childhood asthma and also a predictor of persistence of childhood asthma into adulthood. The “atopic march” is a well recognized phenomenon in which children develop atopic dermatitis and/or food allergy in early childhood, and then go on to have recurrent wheezing and persistent atopic asthma in later childhood and adulthood. Our selection of specific hypotheses for examination in Project 500 reflects this phenomenon.

Four specific hypotheses will be tested in “Project 500”:

1. **Maternal diet in pregnancy influences food sensitization in infancy; specifically avoidance of foods (e.g. peanuts) is associated with intolerance to that food.**

Research on diet and interventions to prevent atopic disease have focused on foods with anti-inflammatory properties (e.g. n-3 fatty acids), antioxidants (vitamin E and zinc), and vitamin D. Recent

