Study Design	
CHILD Study Methods: Pregnant women from the general population were recruited in the second and third trimester of pregnancy in multiple urban and rural centres; they reflect ethnically, environmentally, socioeconomically and culturally diverse families with over 25% non-Caucasian parents. Children currently range from those recently born up to 5 years old.
 
Children are assessed at delivery, at a 3-month home visit, and at 1, 3, and 5 years of age. Repeated and diverse environmental and health questionnaires combined with objective measurements (allergy skin prick tests, lung function) detailed home inspection, and a rigorously annotated bank of biological samples from parents (venous blood, breast milk), index child (cord and venous blood, stool, urine, nasal secretions) and home (dust) provide a robust, comprehensive database for testing of multiple interrelated hypotheses.
 
Specific methods pertinent to the current analyses:
 
Data entry related to events prior to the 1 year assessment have been completed as a priority for these 500 children, and data entry for all 1 year questionnaires and samples given priority. Questionnaire data will then be accessed from HealthDiary, cleaned and assembled by an experienced Data Manager. 500 dust samples and 1500 blood samples (mother, cord blood, child at 1 year) will be identified and retrieved for analyses. Dust analyses will be undertaken at the laboratory of [name], University of Toronto, and blood analyses at the Clinical Trials and Clinical Research Laboratory, Hamilton. Teams of CHILD investigators will analyze the resulting data in collaboration with local statisticians and with our Senior Statistician, [name], Canada Research Chair in Statistical Methods for Health Care, University of Toronto.
 
[1] Maternal diet in pregnancy influences food sensitization in infancy, specifically avoidance of foods (e.g. peanuts) is associated with intolerance to that food.
 
Pre- and post-natal nutrition has been collected using maternal and infant/child questionnaires including exclusive and non-exclusive breast-feeding, age of first supplementation and age of introduction of solid foods. A Food Frequency Questionnaire (FFQ) developed by nutritional epidemiologists at the Fred Hutchinson Cancer Research Center, based on questionnaires used in US studies was modified to reflect Canadian ethnic food choices. Further, the database developed by the University of Minnesota Nutrition Data Systems for Research for data entry and nutrient analysis was “Canadianized” for use in CHILD. This self-administered FFQ asks pregnant mothers to report the frequency of consumption and portion size of approximately 175 line items during their pregnancy, and was completed by the mother at the time of enrollment. At age 3 and 6 months and 1 year, child diet was recorded, including exposure to cow’s milk, eggs and nuts.
 
[2] Low serum 25-hydroxyvitamin D values in infancy are associated with development of early childhood wheezing.
 
Serum is obtained from children at age 1 year; vitamin D will be measured by standard assay methods at the research laboratories at the Hospital for Sick Children. Recurrent wheezing will be identified from questionnaires completed by mother when the child is 3, 6 and 12 months of age.

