Statistical justification for the study design, sample size calculation, and statistical analysis plan	
For Project 500, we have selected 500 children in whom we now have complete data to age 1 year. These will comprise approximately 125 children from each of the recruitment sites to minimize geographic bias. At age 1 year, the dominant clinical outcomes of relevance are wheezing (as defined as a positive response to ever wheeze on 3, 6 or 12 month questionnaires), atopic dermatitis and reported food allergy, and objective evidence of sensitization to food and inhalant allergens assessed by skin testing (≥ 2mm wheal response to epicutaneous testing). We currently have little information on biological data at 1 year, as it is rare for normal children to have blood taken at this age. It is even less common to have a population of healthy normal children providing blood, urine, stool, nasal secretions, and skin allergy tests, to examine correlates of biomarkers with these outcomes. Hence power calculations for this sample of 500 are difficult, but the planned analyses will provide preliminary data which will allow calculations of appropriate sample sizes for future analyses in the full cohort. We anticipate approximately 50 of these 500 children will have experienced wheezing in the first year of life, and a similar number will have developed atopic dermatitis.
 
For the full CHILD Study, the primary outcome is physician-confirmed asthma at age 5 years, with multiple pre-specified intermediate and secondary outcomes. Recruitment and follow-up of over 3,000 families from the general population will allow well-powered integrated analyses involving derivation of new multi-exposure indices; examining the effect of respiratory infections on growth of infant pulmonary function; identification of innate and adaptive immune phenotypes in relation to environmental exposures; linkage of epigenetic profiles to maternal stress, socioeconomic status, environmental exposures and viral infections; and determining impact of nutritional factors including maternal diet, breast-feeding, infant diet, transition to table foods and the role of probiotics and nutraceuticals on immune function through the infant microbiome. The comprehensive longitudinal assessments within CHILD allow sophisticated statistical modeling, including longitudinal latent class analysis, structural equation modeling and factor analysis to assess specific pathways relating genetics, SES, immunity, environment and nutrition to the development of allergy and asthma.
 
The statistical analyses for Project 500 will include a number of statistical approaches, including logistic regression (Agresti, 2012), generalized linear models, and generalized linear mixed models (McCulloch et al., 2008). Both

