
	
univariate and multivariate analyses will be employed, and the effects of potential confounders will be investigated through multivariable analyses.
 
All exposure and outcome variables will be first examined, prior to statistical modeling. For continuous measures (e.g. vitamin D intake during pregnancy in Hypothesis 1, serum 25-hydroxyvitamin D in infancy in Hypothesis 2, indoor concentrations of endotoxin and β-glucans in Hypothesis 4), the distributions (including mean, median, range, variance, etc) will be described and then used for determining the appropriateness of possible modifications to measures (e.g., log transformation for non-normality, or categorizing values using cut-offs based on both statistical and clinical/biological reasons); for categorical measures (e.g., development of wheezing at 1 year in Hypothesis 2, positive results for peanut sensitization in skin tests in Hypothesis 3, and development of atopy at 1 year in Hypothesis 4), frequencies and percentiles will be summarized and used to determine choices of statistical methods (e.g., exact methods for sparse data, if applicable).
 
Specifically, for Hypothesis 1, the association between intolerance to certain foods (e.g. peanut) and maternal diet (e.g. exposure to nuts) will be examined first using bivariable logistic regression analysis; here the outcome (binary) variable is intolerance (e.g. to peanuts, yes/no), and the explanatory variable is diet (e.g. avoidance of peanuts, n-3 fatty acid intake), which can be either a binary (yes/no), a categorical (low/medium/high) or a continuous variable. When considering the effects of covariates, such as gender and maternal atopy, on the association being investigated, multivariable logistic regression analysis will be employed, and potential confounders such as ethnicity will be accounted for in the regression model.
 
Similar approaches will be employed in the analyses of the other hypotheses. For Hypothesis 2, the outcome variable, development of early childhood wheezing (yes/no), will be determined at 1 year, and the measure of serum 25-hydroxyvitamin D status [25(OH)D] will be examined for its distribution and, if necessary, categorized as an ordinal variable (e.g. low/medium/high based on statistical and clinical/biological thresholds). Results based on ordinal categorization will likely provide an intuitive interpretation of the association (e.g. quantifying an n-fold increase in risk for developing childhood wheezing when comparing high vs. low 25(OH)D). As a primary exposure variable of interest, the distributions of 25(OH)D values will be compared between two groups, infants with vs. without wheezing, using nonparametric methods (e.g. Wilcoxon rank-sum test) and the t-test (if normally distributed); if the distribution exhibits a categorical trend, the chi-square test will be applied to evaluate the relationship with the outcome (childhood wheezing).
 
For Hypothesis 3, the association between the outcome variable, wheezing episodes in early infancy (any wheeze to 1 year), and sensitization to foods (positive test result) will be examined using regression models for categorical data. As described in the previous section “Study Design”, sensitization will be defined as a binary variable (positive/negative), and test results for single and multiple foods (e.g. sensitivity to egg and peanut) will be considered in the analyses, which will employ multiple indicators (so-called “dummy variables” for each of the foods tested). To investigate whether there are additive effects that combinations of sensitizations to different foods have on the frequency of

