--	--

	
wheezing episodes, the generalized linear models and the generalized linear mixed models will be utilized.
 
When considering the exposures to oxidizing agents under Hypothesis 4, the primary outcome variable is the development of atopy and wheeze at 1 year (binary, yes/no). The relationships between the outcome and the various outdoor and indoor exposures (e.g., home dust mite allergens, continuous variable; pet ownership, categorical variable) described in the Study Design will be investigated using multivariable logistic regression analyses. The effects of other variables, such as genetics and psychosocial stress, will be examined in the regression model as covariates.
 
For all four specific hypotheses, the statistical evaluations will include univariate (e.g. distribution of 25(OH)D), bivariate (e.g., association between sensitization to peanut and childhood wheezing), and multivariate (e.g., relationship between the development of early childhood wheezing and low serum 25(OH)D value while controlling for birth weight) analyses. Variable selection, including possible interactions (effect modifications) between variables, for the multivariable regression models will be adjudicated based on both statistical and clinical significance, and the final model will be determined using the Akaike Information Criterion and the Hosmer and Lemeshow goodness-of-fit test (Hosmer and Lemeshow, 2000).
 
All of the approaches mentioned above can be readily implemented using SAS (v9.3) and/or R (v2.15).

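### The primary wheeze outcome is recurrent wheeze in the objective and the Hypothesis 2 methods, but the statistical section defines and models ever/any wheeze, so the yes/no models do not address the outcome as stated

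*Protocol*

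**What the plan says.** The protocol describes the wheeze outcome in several places.

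- **Purpose and rationale, objective of Project 500:** the "primary clinical outcomes are recurrent episodes of wheezing and development of atopy by age 1 year".
- **Study Design, item 2 (Hypothesis 2):** "Recurrent wheezing will be identified from questionnaires completed by mother when the child is 3, 6 and 12 months of age". The number of episodes, or the way the three questionnaires combine, is not stated.
- **Statistical justification row, opening paragraph:** "wheezing (as defined as a positive response to ever wheeze on 3, 6 or 12 month questionnaires". One positive answer is enough.
- **Same row, expected events:** "We anticipate approximately 50 of these 500 children will have experienced wheezing in the first year of life".
- **Same row, Hypothesis 2:** the outcome is "development of early childhood wheezing (yes/no), will be determined at 1 year".
- **Same row, Hypothesis 3:** the outcome is "wheezing episodes in early infancy (any wheeze to 1 year". A follow-on analysis reads "To investigate whether there are additive effects that combinations of sensitizations to different foods have on the frequency of" wheezing episodes, using generalized linear and generalized linear mixed models.
- **Same row, Hypothesis 4:** "the primary outcome variable is the development of atopy and wheeze at 1 year (binary, yes/no".

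The word recurrent does not occur in the statistical row.

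**The concern.** Recurrent wheezers are a subset of ever-wheezers. The two definitions therefore give different case sets from the same questionnaires, and they differ by exactly the children who wheezed once. For Hypothesis 2 the conflict falls within a single test: the methods text promises recurrent wheezing and the analysis text models wheezing yes/no.

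Three of the four hypotheses rest on a wheeze outcome. If the statistical section is followed, the odds ratios describe any wheeze, while the protocol's named primary outcome is recurrent wheeze. The protocol also says the results will inform sample sizes for the full cohort, so a rate or effect carried forward under the wrong label would affect later planning. The 500 children already have their required data, so the definition needs to be settled before exposures and outcomes are joined.

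**Working it through.** **Step 1: the texts side by side.**

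| Place | Wheeze outcome | Recurrence required? | Operational rule? | Expected count? |
|---|---|---|---|---|
| Objective of Project 500 | recurrent episodes | yes | no | no |
| Study Design, Hypothesis 2 | recurrent wheezing | yes | no | no |
| Statistical row, definition | ever wheeze | no | yes: any one of three questionnaires | about 50 of 500 |
| Hypothesis 2 analysis | wheezing yes/no | no | as above | as above |
| Hypothesis 3 main analysis | any wheeze to 1 year | no | as above | as above |
| Hypothesis 3 follow-on | frequency of episodes | not applicable | no | no |
| Hypothesis 4 analysis | atopy and wheeze, yes/no | no | as above | none for the pair |

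No yes/no model for Hypotheses 2 to 4 is specified on recurrent wheeze.

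**Step 2: the plan's own figure.** 50/500 = 10% with any wheeze. The protocol gives no alpha, power or effect size, so there is no power statement to reproduce or contradict.

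**Step 3: scale, for illustration only.** Assumptions not in the protocol: 25% of children exposed, two-sided 5%, 80% power, and 25% to 50% of the 50 ever-wheezers recurrent. Recurrent events would then be 0.25 × 50 = 12.5 to 0.50 × 50 = 25.

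The detectable odds ratio was found in two ways, both with power = Φ[(d − 1.96·SE0)/SE1], where d is the difference in proportions, SE0 uses the pooled variance and SE1 the unpooled variance.

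- *Comparing risk between exposure groups:* 125 exposed and 375 unexposed, p1 = OR·p0/(1 − p0 + OR·p0), with 0.25·p1 + 0.75·p0 = events/500. For 50 events, p0 = 0.0772 and p1 = 0.1684, so d = 0.0912. SE0 = √(0.1 × 0.9 × (1/125 + 1/375)) = 0.0310 and SE1 = √(0.1684 × 0.8316/125 + 0.0772 × 0.9228/375) = 0.0362. The argument of Φ is (0.0912 − 0.0607)/0.0362 = 0.84, which is 80% power at OR 2.42.
- *Comparing exposure between cases and non-cases:* 25% exposed among non-cases and OR·0.25/(0.75 + OR·0.25) among cases.

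| Events | OR, by risk | OR, by exposure |
|---|---|---|
| 50 | 2.42 | 2.37 |
| 25 | 3.30 | 3.16 |
| 15 | 4.60 | 4.21 |
| 12 | 5.56 | 4.89 |

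**Step 4: dilution, for illustration only.** This further assumes that the exposure has no effect on single-episode wheeze. Exposure among recurrent cases is q1 = OR·0.25/(0.75 + OR·0.25), which is 0.40 at OR 2 and 0.50 at OR 3. With recurrent share s, exposure among all ever-wheezers is m = s·q1 + (1 − s)·0.25, and the ever-wheeze odds ratio is [m/(1 − m)]/(0.25/0.75).

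- True OR 2: s = 25% gives m = 0.2875 and an odds ratio of 1.21; s = 50% gives m = 0.325 and 1.44.
- True OR 3: s = 25% gives m = 0.3125 and 1.36; s = 50% gives m = 0.375 and 1.80.

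**The case against.** The strongest reply is that the hypotheses and the analyses largely agree. None of the four hypothesis statements uses the word recurrent: Hypothesis 2 speaks of early childhood wheezing, Hypothesis 3 of wheezing episodes, Hypothesis 4 of atopy and wheeze. The mismatch lies in one objective sentence and one methods sentence. Ever wheeze is also the only definition with a working rule, so there is one specified outcome and one undefined label. The project is observational and described as preliminary, and a detailed recurrence rule could sit in an analysis plan not shown here.

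Most of this is fair, and it limits the point. It does not remove it. The objective sentence is the one that names the primary outcomes, and the conflict is between two statements in the current text, not a detail left for later.

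A reader might infer three stronger things that the protocol does not support:

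- *That the analyses cannot support any conclusion on the primary outcomes.* Atopy is the other primary outcome and is untouched, and the Hypothesis 3 follow-on goes beyond ever/never by modelling episode frequency.
- *That the final report will claim effects on recurrent wheeze.* No text says so; the risk is that the mismatch allows it.
- *That a stated power is undermined.* None is claimed, and the protocol itself says power calculations are difficult.

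**Conclusion.** The inconsistency stands and needs correcting. The protocol makes recurrent wheezing a primary outcome and the Hypothesis 2 outcome, gives no rule for it, and then defines and models ever/any wheeze. As written, the yes/no models for Hypotheses 2 to 4 do not estimate effects on the stated primary wheeze outcome. This rests on the text alone.

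Its numerical size cannot be taken from the protocol, which gives no recurrent share and no exposure prevalence. Under the stated assumptions, the detectable odds ratio is about 2.4 at 50 events, 3.2 to 3.3 at 25, 4.2 to 4.6 at 15 and 4.9 to 5.6 at 12. Each range reflects the two methods of calculation. The dilution figures need the further assumption of no effect on single-episode wheeze. They show the direction and possible scale, and should not be read as estimates for this cohort.

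**What to change.** Before exposures are linked to outcomes, use one wheeze definition in the objective, in the Study Design text and throughout the statistical section.

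- **Simplest option:** restate the primary wheeze outcome in the objective, and the Hypothesis 2 sentence in Study Design, as ever wheeze on the 3-, 6- or 12-month questionnaire. It is the only definition with an operational rule and an expected count. Word conclusions as any wheeze.
- **Recurrent wheeze:** report it as a named secondary outcome with its own expected event count. Base its rule on episode counts or on non-overlapping recall periods. Two positive ever-wheeze answers are not a safe rule: the protocol gives no recall period for that item, so one early episode could be reported again at later questionnaires and counted as recurrent.
- **Alternative:** if recurrent wheeze is to remain primary, define it, make it the outcome of the yes/no models and give its expected count, accepting fewer events.

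The simplest option costs wording changes in the places listed and one extra secondary model per wheeze hypothesis. Its drawback is a primary claim less specific to asthma.

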Title of the Proposal:

"Project 500" CHILD Study

STUDY METRICS:

Planned number of subjects:	In total, the CHILD Study recruited 3,629 families and 3,350 children are currently being followed. We plan to test several key hypotheses by analyzing 1 year outcomes in a subset of 500 children in whom we now have complete datasets to that age.
How long will it take to write and submit protocol to IRB/IEC (in months)?	REB approvals for the full CHILD Study have been received at all four recruitment sites – Vancouver, Edmonton, Winnipeg, Toronto – and at the National Coordinating Centre in Hamilton. All are current. No additional ethical approval is required to undertake the analyses proposed.
Projected Start Date (after IRB/IEC and contracting are complete):	Project 500 will commence as soon as funding is obtained to perform the biological analyses.
Expected accrual rate (# of subject/month):	Recruitment of the full CHILD cohort was completed in 2012.
Projected enrollment timelines: Please specify - Date first subject enrolled (mm/yyyy): - Date Last subject enrolled (mm/yyyy): - Follow-up time (in months):	The cohort is fully enrolled. The 500 children selected for this project have all the required data and samples now available. Follow-up of all CHILD subjects is planned until infants are aged 5 years but this specific project is examining outcomes in the first year of life.
Target time of the first formal analysis (mm/yyyy):	June 2015
Target time of the final report (mm/yyyy):	June 2016
Time to generate draft manuscript or poster/abstract (in months):	3 months
Target Publication or Conference (include mm/yyyy):	Data will be presented at national (AllerGen, CSACI) and international (ATS, ERS) conferences 2015-16.

Purpose and rationale for the study:

This proposal relates to the testing of several specific hypotheses in a subset of 500 participants in the Canadian Healthy Infant Longitudinal Development (CHILD) Study. These 500 now have complete data from the time of recruitment (in pregnancy) to age 1 year. The primary purpose of this proposal is to identify risk factors for early allergic outcomes and biomarkers that may predict future disease. These 500 infants will provide critical preliminary data, not only related to early outcomes, but also to inform analytical plans for the full CHILD cohort.

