Recent studies suggest that early-life exposure to ambient air pollution may also contribute to the development of asthma, with traffic-related air pollution (TRAP) likely playing an important role. TRAP represents a complex mixture of pollutants (particulate matter, nitrogen oxides, carbon monoxide, organic compounds) in concentrations that are variable over short distances, but that also build-up over parts of the city contributing to a variable urban background. Respiratory health risks are generally highest among those living close to busy roads with significant truck traffic, but concentration variations across urban areas have also been associated with incident asthma. The effects of TRAP on airways disease likely also depend on poorly understood interactions with a range of endogenous or exogenous factors such as genetics, co-exposures such as allergens and environmental tobacco smoke, and psychosocial stress. The CHILD Study provides an opportunity to study TRAP in four major cities with highly variable and well-characterized concentrations, and to examine relationships between TRAP, indoor air contaminants, and development of wheeze and atopy in early childhood with the intent of following these children through childhood to determine asthma outcomes.

Description:

Primary Objective(s) and Endpoint(s), if different from objective(s)	
The primary objective of the full CHILD Study is to better understand key relationships and interactions among the many genetic determinants and environmental exposures associated with the development of childhood asthma, and use this understanding to prevent it and improve its treatment. Identification of causal pathways will lead to development and implementation of preventative and therapeutic strategies to reduce morbidity and even mortality of childhood asthma.
 
The primary objective of Project 500 is to analyze multiple clinical and environmental questionnaires and selected infant biological samples to determine predictors of early clinical outcomes related to allergy and asthma, utilizing a subset of children who now have complete data to age 1 year.

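### The biomarker aim is predictive power, but the analysis section gives only association methods and an in-sample model-choice rule, so predictive power is never validly estimated

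*Protocol*

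**What the plan says.** Three places in the protocol use the language of prediction:

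- Purpose and rationale, general statement: "The primary purpose of this proposal is to identify risk factors for early allergic outcomes and biomarkers that may predict future disease".
- Purpose and rationale, objective of Project 500: after exploring patterns of illness, the investigators "will correlate these with analysis of multiple biomarkers to determine their predictive power".
- Primary objective: the data are analysed "to determine predictors of early clinical outcomes related to allergy and asthma".

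The protocol has its own section on sample size and statistical analysis. It lists logistic regression, generalized linear and mixed models, the Wilcoxon and t-tests, and the chi-square test. The closing rule, given for the multivariable models of all four hypotheses, is that "the final model will be determined using the Akaike Information Criterion and the Hosmer and Lemeshow goodness-of-fit test". Before that step, the choice of variables and interactions "will be adjudicated based on both statistical and clinical significance". The section names no measure of discrimination, no hold-out sample, cross-validation or bootstrap, and no shrinkage or correction for optimism.

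On size it says "we have selected 500 children in whom we now have complete data to age 1 year" and "We anticipate approximately 50 of these 500 children will have experienced wheezing in the first year of life". It does not say how many biomarkers will be candidates.

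**The concern.** Predictive power is a quantity: how well the marker or model separates children who do and do not have the outcome, and whether its predicted risks hold in children not used to build it. An association test does not give that quantity. Nor do the two criteria named for the final model. AIC ranks candidate models against each other but does not say whether the best one predicts usefully. Hosmer-Lemeshow compares observed and fitted risks in the children used for fitting, and a model with no discrimination can pass it easily.

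The protocol means these results to shape analysis plans and sample sizes for the full cohort. If a biomarker is called predictive because it survived selection and the model fitted acceptably, an optimistic impression carries into that larger work. With about 50 events there is little information to protect against this.

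**Working it through.** The protocol gives no performance or power figure to reproduce. Its only numerical anchor is about 50 wheezers in 500, that is 50/500 = 10%.

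**Step 1. What AIC does with a noise term.** Removing one single-parameter term changes AIC by the likelihood-ratio statistic minus 2, so the term stays if that statistic exceeds 2. For a noise term the probability is P(chi-square with 1 df > 2) = 0.157.

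**Step 2. Chance that at least one noise term stays.** With m independent candidates this is 1 − (1 − 0.157)^m. Events per candidate are 50/m.

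| Candidates m | P(at least one kept) | Events per candidate |
|---|---|---|
| 1 | 0.16 | 50 |
| 4 | 0.50 | 12.5 |
| 10 | 0.82 | 5 |
| 20 | 0.97 | 2.5 |

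**Step 3. How the selected models look.** Simulation: 500 children, exactly 50 events, m independent standard-normal markers unrelated to the outcome, backward elimination by AIC. The AUC computed in the same children (apparent AUC) is compared with the true value of 0.50. The value of m is assumed. The range starts low because the wheeze hypotheses name few markers: one 25(OH)D measure in Hypothesis 2 and three food skin tests in Hypothesis 3.

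| Candidates m | Mean apparent AUC (an empty model counts as 0.50) |
|---|---|
| 1 | 0.51 |
| 3 | 0.54 |
| 4 | 0.54 |
| 10 | 0.58-0.59 |
| 20 | 0.63-0.64 |

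The ranges are across separate runs with different random draws. Among only the runs that kept at least one marker, the means were 0.61 for m = 10 (5th-95th percentile 0.56-0.66) and 0.64 for m = 20 (0.59-0.70).

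**Step 4. The same models in new children.** For m = 10, 20 and 30, each selected noise model was applied to 5,000 new subjects. Mean AUC was 0.50 in all three settings.

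**Step 5. Does Hosmer-Lemeshow catch them?** With ten groups, the selected noise models passed (p > 0.05) in 96%, 95% and 94% of cases for m = 10, 20 and 30. A model without discrimination is usually well enough calibrated in its own data, so the test has almost nothing to detect.

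The simulation stands in for a rule that the protocol states only in outline. A strict significance threshold or clinical judgement would remove some noise terms. Correlated markers or tested interactions would change the figures too.

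**The case against.** The case on the other side is substantial.

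- **Assignment.** AIC and Hosmer-Lemeshow are introduced for the four hypotheses, which concern influence, association and risk factors. A reader might infer that the protocol offers them as proof that a biomarker predicts. It does not; they choose the final regression model. This stands. The gap is that nothing else in the section serves the predictive aim.
- **Other guidance.** A reader might also infer that models are judged by in-sample statistics alone. Clinical significance also guides selection. That stands, although clinical judgement is not a measure of prediction.
- **AIC.** It penalises complexity and, for prespecified models, approximates relative out-of-sample fit. True, but data-driven selection weakens that protection, and AIC never states how well the model predicts.
- **Size.** No AUC is planned, so an inflated one is not an output of the plan, and at the 1-4 markers named for wheeze the inflation is small. Both stand. The higher figures show what could happen if many biomarkers are screened, not what will happen.
- **Wording and stage.** Predictor is often used loosely for risk factor, and the work is called preliminary. This softens the general purpose and the primary objective, but less so the explicit aim to determine predictive power. The protocol does not commit to testing these biomarker models in the remaining children. Its plan to validate the Asthma Predictive Index concerns an existing index at later follow-up.
- **Detail for a separate SAP.** A c-statistic or bootstrap can be specified there, and that document is not at hand. But this protocol carries its own analysis-plan section and fixes the model-choice rule, so the mismatch with the aim is visible in the protocol itself.

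**Conclusion.** The point holds for the biomarker aim only. The protocol sets out to determine predictive power, and the methods it fixes do not estimate it. The association analyses for the four hypotheses are not undermined; a reader who concluded that they were would go beyond the documents.

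The possible size runs from slight to moderate: a mean apparent AUC of about 0.51-0.54 for 1-4 noise candidates and about 0.58-0.64 for 10-20, against a true 0.50. These figures assume 50 events in 500, independent continuous markers and backward AIC selection; the number of markers is not in the protocol. That AIC and Hosmer-Lemeshow do not measure discrimination needs none of these assumptions. This is an inexpensive improvement that should be made, not a fatal defect.

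**What to change.** For the biomarker aim in the purpose and rationale section, do one of two things.

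1. **Estimate prediction.** Report the c-statistic, or its gain over a prespecified clinical model, together with the calibration slope. Correct both for optimism by a bootstrap that repeats every selection step in each resample. Base any statement on predictive power on these corrected figures, not on AIC or Hosmer-Lemeshow. A penalised fit is optional, and the choice of clinical model is the investigators'.
2. **Restate the aim.** Describe the biomarker work as association screening, with predictive performance to be tested in the rest of the cohort.

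The first option costs a little more analysis code in SAS or R, which the protocol already names, and the reported performance will be less favourable. The second costs only wording. Neither needs new data or samples in Project 500, or any change to the four hypothesis tests.
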